12. REPORTING CONVENTIONS

P-values ≥ 0.001 and ≤ 0.999 will be reported to 3 decimal places; p-values less than 0.001 will be reported as “ <0.001 ”. The mean, standard deviation, and other statistics will be reported to 1 decimal place greater than the original data. The minimum and maximum will use the same number of decimal places as the original data. Proportions will be presented as 2 decimal places; values greater than zero but <0.01 will be presented as “ <0.01 ”. Percentages will be reported to the nearest whole number; values greater than zero but $<1\%$ will be presented as “ <1 ”; values greater than 99% but less than 100% will be reported as “ >99 ”. Estimated parameters, not on the same scale as raw observations (e.g. regression coefficients) will be reported to 3 significant figures.

13. TECHNICAL DETAILS

SAS version 9.4 or above will be used to generate all tables, figures and listings or R version 4.1.1 or higher.

14. SUMMARY OF CHANGES IN THE CONDUCT OF THE STUDY OR PLANNED ANALYSES

14.1. Changes in the Conduct of the Study

14.1.1. Protocol Amendments

The first subject enrolled on protocol version 2.0. Subjects were also enrolled on protocol version 3.0. Substantive changes between these protocol versions are summarized below.

- Day 28 Visit will not reflect completion of treatment phase as subject will have to take the final dose after the visit. Treatment phase description was updated to reflect number of doses.
- The following stool related exploratory outcome measures and urine sensitivity outcome measures were added:
 - The effect of co-pathogens, as determined by the BioFire stool pathogen screen, on the primary outcome measure.
 - Time from randomization until initial clinical resolution of Norovirus symptoms for at least 48 hours through Day 180. Clinical resolution will be assessed from the daily diary by the subject and will be defined as cessation of vomiting and no stools classified by the Bristol Stool Chart as diarrhea (Type 6 or 7) from the total population compared to the subgroup of subjects who do not report chromaturia (discoloration of urine) based on unsolicited self-reporting.
 - Incidence of unsolicited non-serious adverse events (see section 9 for details) through 60 days, laboratory adverse events (WBC, Hemoglobin, Platelet count, Creatinine, Alkaline Phosphatase, ALT, AST, BUN and Bilirubin) through 60 days, protocol-specified serious adverse events (see section 9 for details) through 60 days, and Hospitalization through 60 days from the total population compared to the subgroup of subjects who do not report chromaturia (discoloration of urine) based on unsolicited self-reporting.
 - Time from the randomization to first negative viral load through 180 days and the change in viral titer between Day 1 and 180 from the total population compared to the subgroup of subjects who do not report chromaturia (discoloration of urine) based on unsolicited self-reporting.
- Addition of a \pm 3-day window for the Study Day 35 call.

14.1.2. Study Product Administration

One site (University of Nebraska) received multiple kits representing one study product and no kits of the other study product when it ordered study product from the DMID Clinical Materials Services contractor. Due to this imbalance, the online randomization module in Advantage eClinical would have prevented randomization if it was attempted. To resolve the issue, the site was instructed to order additional kits, although they described their inventory as sufficient. The site was informed a second time that the number of kits they had on-site were insufficient and they would not be able to randomize unless they ordered more kits. The site subsequently agreed to order additional kits. This communication was considered by the SDCC to meet the definition of an accidental partial unblinding as it could be inferred that all the kits on-hand were identical. To address the issue, the MOP was updated to instruct sites to always order a minimum number of kits in addition to always maintaining a number of kits on-site. No changes to planned analyses were made in response to this situation.

14.1.3. Daily Diary Completion Time

Subjects were instructed to complete their daily diary at the same time each day. During manual review of the data, it was discovered that subjects had entry dates with morning diary times and/or diary times that were <12 hours from their previous entry's diary time. Given the inconsistencies in the timing of the daily diary entries, it is difficult to know if subjects were recording information for the previous study day or the prior 24 hours. For diary entries that are <12 hours apart, it is likely that information has been duplicated. The analyses assume that the data reflected in each diary is for the date of diary completion; however, this is a limitation that was not able to be resolved during the study. The number of diaries completed in pre-specified windows (12pm – 6am, 6pm – 12am, 12am – 6am, and number completed less than 12 hours after previous diary completed) is provided in Listing 10.

14.2. Changes in Planned Analyses

It was originally planned that the study would enroll 160 subjects allowing for larger sample statistical methods to be used; however, due to early closure of the study only 31 subjects enrolled. Therefore, it is anticipated that many of these tests will no longer be valid. Many of the analyses from the protocol have been updated to employ small sample techniques and will be primarily descriptive.

16. LISTING OF TABLES, FIGURES, AND LISTINGS

Table, figure, and listing shells are presented in Appendices 1, 2, and 3.

APPENDICES

9.5.1 Efficacy/Immunogenicity and Safety Measurements Assessed and Flow Chart

Table 1: Schedule of Study Procedures

[Implementation Note: Include a graphic display of the frequency and timing of efficacy and safety measures including visit numbers. The schedule of procedures from the protocol may be excerpted and included here, as appropriate.]

Phase	Treatment Phase						Longitudinal Monitoring Phase							
	Screen/Enroll/Day 1	Day 7 (±3 d)	Day 14 (±3 d)	Day 21 (±3d)	Day 28 (+3 d)	Day 35	Day 53 (± 7d)	Day 60 (±14 d)	Day 113 (± 7d)	Day 120 (±14 d)	Day 173 (± 7d)	Day 180 (±14 d)	Unscheduled Visit	Early Termination visit
Visit	01	02	03	04	05	06	07	08	09	10	11	12		
Consent ¹	X													
Urine Pregnancy ²	X													
WBC, TLC, Hb, Platelets ^{3#P}	4 mL ^P	4 mL ³			4 mL ³							4 mL ³		4 mL ³
Creatinine, Alk Phos, AST, ALT, BUN, Bilirubin, ^{3CP}	4.5 mL ^P	4.5 mL ³			4.5 mL ³							4.5 mL ³		4.5 mL ³
T-Cell Subsets ³	4 mL											4 mL		4 mL
Pill Count		X	X	X	X			X ¹⁰						
Vital Signs*	X	X	X	X	X			X		X		X	X	X
Medical History	X													
Physical Exam	X				X									
Inquiry about hospitalization since last Assessment		X	X	X	X	X		X		X		X		X
Stool for Pathogen Screen ⁴	X	X ⁷	X ⁷	X ⁷	X ⁷			X ⁷		X ⁷		X ⁷	X ⁷	X ⁷
Stool Norovirus Testing	X ^{8#}	X ⁴	X ⁴	X ⁴	X ^{8#}			X ^{8#}		X ⁴		X ⁴	X ⁴	X ⁴
Stool Ig Study	X		X ⁴		X			X		X ⁴		X ⁴		X ⁴
Serum Ig Study	10 mL				10 mL			10 mL				10 mL ⁴		10 ⁴ mL
Buccal Swab/Saliva Collection	X													
Randomization	X													
Nitazoxanide PK ⁴		4.5 mL		4.5 mL										

Phase	Treatment Phase						Longitudinal Monitoring Phase								
Procedure	Screen/ Enroll/ Day 1	Day 7 (±3 d)	Day 14 (±3 d)	Day 21 (±3d)	Day 28 (+3 d)	Day 35	Day 53 (± 7d)	Day 60 (±14 d)	Day 113 (± 7d)	Day 120 (±14 d)	Day 173 (± 7d)	Day 180 (±14 d)	Unscheduled Visit	Early Termination visit	
Nitazoxanide or placebo ⁵	X	X	X	X	X										
Return residual medication					X										X
Review concomitant medications	X	X	X	X	X	X		X		X		X			X
Assess for adverse events		X	X	X	X	X		X					X		X
Administer Detailed PROs Packet	X				X			X		X		X			X
Administer Weekly Packet	X	X	X	X	X	X	X	X	X	X	X	X	X		X
Collect Daily Diary ⁶		X	X	X	X			X		X		X	X		X
Phone Call for Status Update						X	X		X		X				
Phone Call for Appt Reminder							X		X		X				
Total Blood Volume	22.5 mL	13 mL	--	4.5 mL	18.5 mL	--	--	10 mL	--	--	--	22.5 mL	--	--	22.5 mL

¹Consent/Accent must be obtained from eligible subjects, consistent with local IRB policy for consent and assent of subjects and must be obtained prior to any study procedures being performed

² Urine pregnancy test will be obtained from women of childbearing potential, results of test must be known and negative prior to dosing.

³Locally performed assay; values obtained within 7 days of the study visit, if obtained for clinical indication, can be utilized during the treatment phase and within 14 days of the study visit for the longitudinal monitoring phase. T cell subset will be drawn unless CBC shows an ALC<100.

⁴ The PK specimen on Day 7 will be collected 1-4 hours after the subject takes the study dose and on Day 21 will be a pre-dose trough and will be drawn only in subjects consenting to this optional assessment.

⁵ Nitazoxanide or placebo kit will be provided to the subject. Study drug (Nitazoxanide or placebo) given BID for 28 days.

⁶ Diary recorded once a day during the treatment phase and once a day during the longitudinal monitoring phase. Copies of completed pages are collected at each study visit. One pack give an enrollment and additional copies provided at Day 28.

⁷ Stool for pathogen screen will not be performed for formed stool except on Day 1 and 180. An aliquot will be retained for later testing if indicated. Norovirus testing includes quantitative viral load at all time points.

⁸ Sequencing at selected time points.

¹⁰Day 60 pill count only needs to be conducted if the dosing was not completed and medications returned during Study Day 28.

⁸ If diarrhea recurs after stopping therapy, would have subject provide a stool specimen for pathogen screen and Norovirus PCR; therapy is at the discretion of the site.

⁹ The sample must have been produced within 24 hours of the visit and if it exceeds 24 hours it must be disposed. After collection in the stool hat, the subjects can wipe down and disinfect the outside of the container and place it in a bag for transport then refrigerate until they come to their visit with the research staff. Subjects would be encouraged to provide another sample within the visit window and if not, rectal swab may be used for all assays related to stool collection.

*Vital Signs include weight, Blood Pressure, Respiration, Pulse, Temperature and Height. Height is only measured at Screening/Enrollment/Baseline visit.

#Derived from Complete Blood Count.

^eDerived from Complete Metabolic Panel.

^fSpecimen also stored for future use.

^gMust be within 3 days of enrollment

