7.1 Screening/Baseline/Treatment Phase

Any subject ≥ 12 years of age, recipient of a solid organ or hematopoietic stem cell transplant with a positive test for Norovirus within 7 days as part of routine clinical care will be approached to participate in the study. Once consent is obtained, then laboratory testing and medical history will be reviewed to determine eligibility unless local IRB waiver allows to review data prior to consent. Assessment required for eligibility may not be measured more than twice.

a. Screening/Enrollment/Baseline

- Consent/Assent will be reconfirmed with eligible subjects, consistent with local IRB policy for consent and assent of subjects.
- Subject and their chart will be reviewed to collect a medical history, concurrent medications.
- Urine pregnancy test will be obtained from women of childbearing potential. Results must be known and negative prior to dosing.
- WBC, TLC (Total Lymphocyte Count) Hb, Platelets (Derived from Complete Blood Count -within 3 days of enrollment).
- Creatinine, Alk Phos, AST, ALT, BUN, Bilirubin (Derived from Complete Metabolic Panel-within 3 days of enrollment).
- T Cell Subsets will be drawn unless CBC shows an ALC <100 .
- Samples to be sent to the central laboratory are collected and processed:
 - Buccal swab and saliva samples for secretor assay.
 - Stool for quantitative Norovirus RT-PCR and sequencing.
 - Stool for other pathogen testing.
 - Stool for Norovirus-specific IgA, IgG, and IgM studies.
- Serum for quantitative Norovirus-specific IgA, IgG, and IgM and total IgG.
- Randomization.
- Vital signs will be obtained (pulse, temperature, BP, respiration, height and weight).
- Weekly Recall Packet will be administered.
- Detailed Subject Reported Outcome and Severity Score Assessment.
- Physical examination will be performed.

- Plastic bag with two 30-count bottles of study product will be dispensed to the subject. The first dose of study product (nitazoxanide or placebo) will be given by the study team.

The study product (nitazoxanide or placebo) will be taken by the subject twice daily for 28 days.

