Subjects will be given a paper diary (to inquire about symptoms and severity along with overall well-being) that will be completed daily, at the time of study product dosing. The time of study product dosing will also be recorded. This will be completed on a daily basis through day 28. The pack of paper diary along with instructions that is given at enrollment will cover the entire study period.

The stool sample must have been produced within 24 hours of the visit and if it exceeds 24 hours it must be disposed. Subject would be encouraged to provide another sample within the visit window and if not, a rectal swab may be used for virus detection.

b. Study Day 7 ± 3 days

- Collection and review of completed diary pages.
- WBC, TLC, Hb, Platelets (Derived from Complete Blood Count).
- Creatinine, Alk Phos, AST, ALT, BUN, Bilirubin (Derived from Complete Metabolic Panel).
- Pill count to assess adherence.
- Samples of stool (collected at home or at clinic) to be sent to the central laboratory are collected and processed:
 - Stool for quantitative Norovirus RT-PCR and sequencing.
 - Stool for other pathogen testing; stool will be stored for later testing and this assay will not be performed for formed stool after Day 1.
- Nitazoxanide PK drawn 1-4 hours after the subject takes his/her dose, for subjects consenting to this optional assessment. The time of the blood draw and the time of the previous dose will be recorded.
- Vital signs (temperature, BP, respiration, weight and pulse) will be obtained.
- Weekly Recall Packet will be administered (Table 5).
- Collect concurrent medications.
- Inquiry about hospitalization since last assessment.
- Assess for adverse events.

c. Study Day 14 ± 3 days: Virtual Visit

- Team to call subject

- Review of completed diary pages.
- Subject to collect stool sample and store in freezer until day 28 study visit
- Weekly Recall Packet will be administered (Table 5).
- Collect concurrent medications.
- Inquiry about hospitalization since last assessment.
- Assess for adverse events.

d. Study Day 21 ± 3 days- Virtual Visit except for patients who agree to optional PK study

- Team to call subject not enrolled in the PK Sub Study (those patients will have in person visit)
- Review of completed diary pages.
- Subject to collect stool sample and store in freezer until day 28 study visit.
- For patients in the PK Sub Study:
 - Samples of stool to be sent to the central laboratory are collected and processed:

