⁶ Diary recorded once a day during the treatment phase and once a day during the longitudinal monitoring phase. Copies of completed pages are collected at each study visit. One pack give an enrollment and additional copies provided at Day 28.

⁷ Stool for pathogen screen will not be performed for formed stool except on Day 1 and 180. An aliquot will be retained for later testing if indicated. Norovirus testing includes quantitative viral load at all time points.

⁸ Sequencing at selected time points.

¹⁰Day 60 pill count only needs to be conducted if the dosing was not completed and medications returned during Study Day 28.

^w Can covert to virtual visit

- § If diarrhea recurs after stopping therapy, would have subject provide a stool specimen for pathogen screen and Norovirus PCR; therapy is at the discretion of the site.
- ¥ The sample must have been produced within 24 hours of the visit and if it exceeds 24 hours it must be disposed. After collection in the stool hat, the subjects can wipe down and disinfect the outside of the container and place it in a bag for transport then refrigerate until they come to their visit with the research staff. Subjects would be encouraged to provide another sample within the visit window and if not, rectal swab may be used for all assays related to stool collection.
- *Vital Signs include weight, Blood Pressure, Respiration, Pulse, Temperature and Height. Height is only measured at Screening/Enrollment/Baseline visit.
- #Derived from Complete Blood Count.
- €Derived from Complete Metabolic Panel.
- ¶Specimen also stored for future use.
- ⓅMust be within 3 days of enrollment. Blood collection includes CBC, Complete Metabolic Panel, T Cell Subsets, and Serum for Ig studies.
- ⁴If Virtual Visit
- ^U If part of PK substudy

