3.3. Study Definitions and Derived Variables

Diarrhea:

Diarrhea will be defined as Type 6 or 7 on the Bristol Stool chart.

Baseline Value:

The baseline value will be defined as the last value obtained prior to the first dose of study product unless otherwise noted.

Additional Nitazoxanide:

Any nitazoxanide reported as a concomitant medication will be considered additional nitazoxanide.

Initial Clinical Resolution of Norovirus Symptoms:

Clinical resolution of Norovirus symptoms will be assessed from the daily diary by the subject and will be defined as:

- Cessation of vomiting and,
- No stools classified by the Bristol Stool Chart as diarrhea (Type 6 or 7).

Subjects will need to have at least two consecutive daily diary entries where they reported no vomiting, no Bristol Stool Type 6, and no Bristol Stool Type 7 to meet the criteria for initial clinical resolution. There are several variables in the daily diary that indicate whether the subject had diarrhea or vomiting for that day.

Daily Diary Diarrhea Questions:

- Phase 1 (Treatment Phase):
 - Number of Bristol Type 6 stools? (Quantitative)
 - Were there too many Bristol Type 6 stools to count? (Qualitative)
 - Number of Bristol Type 7 stools? (Quantitative)
 - Were there too many Bristol Type 7 stools to count? (Qualitative)
- Phase 2 (Longitudinal Phase):
 - Did you have diarrhea today? (By diarrhea, we mean at least ONE bowel movement that could be described as Type 6 or 7.) (Qualitative)

Daily Diary Vomiting Questions:

- Phase 1 (Treatment Phase):
 - Did you have to take another dose because you threw up the first dose within 1 hour? (Qualitative)
 - How many times did you vomit today? (Quantitative)
- Phase 2 (Longitudinal Phase):
 - Did you vomit today? (Qualitative)

For a day to count towards clinical resolution during the treatment phase, the following responses must be recorded in the daily diary entry:

- Both quantitative diarrhea questions must be 0

- Both qualitative diarrhea questions must be missing (i.e. not “yes”)
- The quantitative vomiting questions must be 0
- The qualitative vomiting question must be “no”

For a day to count towards clinical resolution during the longitudinal phase, the following responses must be recorded in the daily diary entry:

- The qualitative diarrhea question must be “no”
- The quantitative vomiting question must be 0

If a daily diary entry is missing, refer to the imputation rules in Section [6.5](#).

Viral Load:

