Number of Type 6 or 7 Stools:

The number of Type 6 or 7 stools through Day 28 will be defined as the sum of the responses to the quantitative Daily Diary Diarrhea Questions during the Treatment Phase (see above). Missing responses will be left as missing.

Number of Days of IV Hydration or Total Parenteral Nutrition (TPN) Therapy:

The number of days of IV hydration or TPN therapy will be defined as the number of days with a concomitant medication with any indication related to IV hydration or TPN therapy. A blinded review of the concomitant medication data will be performed by the Medical Monitor to identify medications that should be included in the analysis. Days prior to Day 1 will not be included in the calculation of the number of days. Medications that are ongoing after Day 28 will be censored at 28 days.

Co-pathogen Status:

Co-pathogen status will be determined by the BioFire stool pathogen screen on Days 1 and 180. Co-pathogen status will be determined on Days 7, 14, 21, 28, 60, 120, and with recurrent diarrhea if unformed stool is present on study day. Analyses will only include whether pathogens were detected or not and will not differentiate by co-pathogen type. The listing will include which co-pathogens were detected at each subject/visit ([Listing 18](#)).

Secretor Status:

Saliva is collected at screening to determine H type 1 secretor status (phenotyping), while a buccal swab is collected to perform FUT2 genotyping. Phenotype and genotype results will either be “secretor” or “non-secretor” for each subject.

Norovirus-Specific Immunoglobulins (Ig):

Results below the lower limit of detection (LLOD) will be imputed as $\frac{1}{2}$ the LLOD. Results above the upper limit of detection (ULOD) will be imputed as the ULOD.

Responders:

A subject is classified as a responder if he or she has a four-fold or greater increase in Norovirus-specific Ig titers compared to baseline (Day 1).

Study Day:

Study day will be reported as the number of days from randomization with the day of randomization reported as study day 1.

Days Post-Randomization:

Days post-randomization will be reported as the number of days since randomization; if an event began on the day of randomization, the days post-randomization is reported as 0.

Duration:

Duration will be reported as the difference between the start and end dates, inclusive of the day the event started.

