14.3.4 Displays of Laboratory Results

14.3.4.1 Chemistry Results

Table 64: Laboratory Results by Parameter, Maximum Severity, Time Point, and Treatment Group – Any Chemistry Parameter

[Implementation Note: Generate one table for “Any Chemistry Parameter” and one table for each chemistry parameter. If a parameter has a grading scale that includes grading for both high and low, then include one column for each severity for high and low, as shown in the second sample table below. If not, then just include one column per severity, as shown in the first sample table. The “Any Parameter” table will just summarize one column per severity.]

Any Chemistry Parameter	Treatment Group	N	None		Mild / Grade 1		Moderate/ Grade 2		Severe/ Grade 3		Missing	
			n	%	n	%	n	%	n	%	n	%
Baseline	Nitazoxanide 500 mg	x	x	xx	x	xx	x	xx	x	xx	x	xx
	Placebo											
Day 7	Nitazoxanide 500 mg											
	Placebo											
Day 28	Nitazoxanide 500 mg											
	Placebo											
Day 180	Nitazoxanide 500 mg											
	Placebo											
Max Severity Post Baseline	Nitazoxanide 500 mg											
	Placebo											

Note: The “Max Post Baseline” rows indicate the maximum severity experienced by each subject at any time point post baseline, including unscheduled assessments.

N = Number of subjects in the Safety Population and in study for the given time point.

Table 65: Laboratory Results by Parameter, Maximum Severity, Time Point, and Treatment Group – Creatinine

Time Point	Treatment Group	N	None		Mild / Grade 1		Moderate/ Grade 2		Severe/ Grade 3		Missing	
			n	%	n	%	n	%	n	%	n	%
Baseline	Nitazoxanide 500 mg	x	x	xx	x	xx	x	xx	x	xx	x	xx
	Placebo											
Day 7	Nitazoxanide 500 mg											
	Placebo											
Day 28	Nitazoxanide 500 mg											
	Placebo											
Day 180	Nitazoxanide 500 mg											
	Placebo											
Max Severity Post Baseline	Nitazoxanide 500 mg											
	Placebo											

Note: The “Max Post Baseline” rows indicate the maximum severity experienced by each subject at any time point post baseline, including unscheduled assessments.

N = Number of subjects in the Safety Population and in study for the given time point.

Tables with similar format:

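### The 7-day look-back for clinical labs lets a blood sample drawn before the first dose be filed as the Day 7 on-treatment safety lab

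*SAP*

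**What the plan says.** **Substitution rule.** Protocol Appendix A puts superscript 3 on the Day 7 blood-draw cell. SAP Table 1 puts it on the Day 7 blood-count and chemistry cells. In the SAP the footnote reads: "values obtained within 7 days of the study visit, if obtained for clinical indication, can be utilized during the treatment phase". The protocol footnote gives the same rule. Neither adds a condition about the first dose.

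**First dose.** It is given at the screening/enrolment/baseline visit, which is Day 1 (Protocol Section 7.1): "The first dose of study product (nitazoxanide or placebo) will be given by the study team".

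**Baseline labs.** These may be taken near enrolment rather than on the day. Protocol Section 7.1 has "Platelets (Derived from Complete Blood Count -within 3 days of enrollment", and Appendix A has "Must be within 3 days of enrollment. Blood collection includes CBC". SAP Section 3.3 then defines the analysis value: "The baseline value will be defined as the last value obtained prior to the first dose of study product unless otherwise noted".

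**Reporting.** The SAP laboratory shells use nominal rows: Baseline, Day 7, Day 28 and Day 180. The summary-statistics shells (SAP Table 78 onwards) add change-from-baseline rows. The severity shells (SAP Table 64 onwards) add a summary row defined as "the maximum severity experienced by each subject at any time point post baseline, including unscheduled assessments".

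**The concern.** A Day 7 safety lab is meant to show what about a week of treatment has done to creatinine, liver tests and blood counts. The look-back for substituted values is 7 days, and a Day 7 visit is only 6 days after randomisation, so the rule can hand back a sample from before treatment began. The baseline window covers some of the same dates, so one clinical draw could fill both rows.

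The opportunity is real. Protocol Section 8.2.1 describes both panels as generally standard of care at transplant centres, and inpatients may be enrolled, so clinically indicated labs around enrolment are to be expected.

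At stake are the Day 7 rows of the safety tables and, through them, part of the evidence on laboratory adverse events through Day 60, a secondary safety outcome.

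**Working it through.** The plan gives no figure to reproduce; this is date arithmetic.

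**Inputs**
- Visit window: "Study Day 7 ± 3 days" (Protocol Section 7.1), so Study Day 4 to 10.
- Day numbering: "Study day will be reported as the number of days from randomization with the day of randomization reported as study day 1" (SAP Section 3.3). Study Day d is therefore d − 1 days after randomisation.
- Look-back: 7 days (footnote 3).
- Baseline lab window: 3 days before enrolment up to the day itself.

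**Formula.** Earliest admissible draw, in days relative to randomisation = (d − 1) − 7 = d − 8.

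| Visit on Study Day | Earliest draw (days from randomisation) | Pre-dose sample possible? | Baseline-window days also admissible for Day 7 |
|---|---|---|---|
| 4 | −4 | yes | −3, −2, −1, 0 |
| 5 | −3 | yes | −3, −2, −1, 0 |
| 6 | −2 | yes | −2, −1, 0 |
| 7 | −1 | yes | −1, 0 |
| 8 | 0 | yes, if drawn on Day 1 before the first tablet | 0 |
| 9 | +1 | no | none |
| 10 | +2 | no | none |

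The window reaches before Day 1 on 4 of the 7 permitted visit days, including nominal Day 7. It admits a pre-dose sample on 5 of 7.

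**Day 28 visit (window +3 days).** 28 − 7 = 21 and 31 − 7 = 24, so the earliest draws fall on Study Days 21 to 24. That visit is not affected.

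**Would a shorter look-back be enough?** For a Day 4 visit the draw must satisfy 3 − L > 0, so L must be 2 days or less. A 3-day look-back still lands on Day 1.

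**Effect on the reported value**
- Same sample x in both rows: change = x − x = 0, and the grade cannot differ from baseline.
- A pre-dose sample earlier than the baseline one: the change need not be zero, but it compares two untreated values.

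**What else is scheduled.** Protocol Section 7.2 lists labs on Days 1, 7, 28 and 180. Protocol Section 9.2.1 and SAP Section 4.5.3 list Days 7, 28 and 60. On either list, Day 7 is the only scheduled post-baseline lab before Day 28. Protocol Section 9.1 also expects Day 60 labs, but the Day 60 visit list and Appendix A schedule none, and those passages need reconciling. By Appendix A, Days 7 and 28 are the only scheduled post-baseline safety labs within the 60-day safety period.

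**The case against.** The best case on the other side is that the rule is permissive, applies only to clinically indicated values, and sits beside a study draw that is already listed for Day 7. That stands. The 5 of 7 counts calendar days, not subjects, and how often substitution occurs is unknown.

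A reader might go further and infer any of the following. The documents do not support them.

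- *The Day 7 lab shows no change by construction.* An exact zero needs the same draw in both rows.
- *The SAP counts a pre-treatment value as post-baseline.* SAP Section 3.3 defines baseline as the last pre-dose value, so a pre-dose draw is not properly post-baseline. What remains is a gap: the rows are nominal, and nothing says that such a value is removed from them. Listings 24 and 25 show both planned time point and actual study day, but do not say whether the latter is the draw date.
- *Early changes will be missed.* Labs done by the clinical team outside study visits are reportable if clinically significant and not attributable to Norovirus or the underlying condition (Protocol Section 9.2.1), and the maximum-severity row takes in unscheduled assessments. This is a narrower filter than a scheduled lab, so the cover is partial, but it exists.
- *Every laboratory adverse event needs a grade shift from Day 1.* In Protocol Section 9.2.3 that rule applies to subjects whose baseline value is out of range, and other criteria are listed.
- *The Grade 3 laboratory halting rule is weakened.* That rule halts further enrolment, and SAP Section 6.6 records that the study stopped after 31 subjects.

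**Conclusion.** The point holds as a gap in a stated rule. Footnote 3 admits a pre-dose sample as the Day 7 lab for visits on Days 4 to 8, reaching back at most four days before randomisation, and the SAP has no step that takes such a value out of the nominal Day 7 and maximum post-baseline rows. A reused baseline sample gives zero change; any other pre-dose sample is still not an on-treatment value.

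This rests on two readings: that the footnote looks backward (it gives no direction, but a plus-or-minus reading includes this), and that the first dose falls on Day 1.

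The number of subjects affected cannot be derived from the documents, so no claim about dilution of an arm difference can be sized. With 31 subjects and 1:1 allocation, and assuming a roughly even split, an arm holds about 15.5 subjects. One misfiled value is then 1/15.5, about 6.5% of an arm's Day 7 row. The analyses are now mainly descriptive (SAP Section 14.2), so the consequence is a misleading table entry rather than a changed test result. It is still worth correcting, because the correction is cheap.

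**What to change.** **In the SAP (Section 9.6 or 3.3), still actionable before the tables are run:** assign laboratory results to analysis time points by actual draw date. Exclude any value drawn before the first dose from the Day 7, change-from-baseline and maximum post-baseline severity rows. State that the actual study day in Listings 24 and 25 is the draw date, and report how many Day 7 values were excluded.

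**In Protocol Appendix A footnote 3 and SAP Table 1 footnote 3, for the record or any reuse of the schedule:** accept a substituted Day 7 value only if it was drawn after the first dose and within Day 7 ± 3. This cannot alter samples already collected.

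**Cost:** one or two sentences in the SAP and one footnote. A few subjects may have a missing Day 7 value. The graded-result shells, such as SAP Tables 64 and 84, already have a column for missing results.
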